1. The principle investigator will screen the potential patients through careful clinical examination of patients at the orthodontic department, Faculty of Oral and Dental Medicine, Future University.

2. All recruited patients should fulfil the previously mentioned inclusion and exclusion criteria.
3. Every participant will be asked to sign an informed consent before the beginning of the study.
4. After patient's enrolment, each participant will be asked for pre-intervention records to ensure proper diagnosis.
5. The supervisor will randomly allocate the patients to one of the intervention groups.
6. Active intervention will begin after proper leveling and alignment of the upper and lower arches and canine retraction.
7. The principle investigator will take pre-retraction records for every participant. (T_0)
8. In Friction mechanics group, Power chain is used for anterior segment retraction while in Frictionless group, T-loop is used for retraction.
9. Each patient will come every 4 weeks for follow up visit, for appliance activation and uptake of impression for interim records.
10. After complete space closure, the principle investigator will take post-retraction records for each participant. (T_{final})
11. Every patient will fill up a questionnaire regarding his experience during treatment.
12. The principle investigator will continue the normal treatment and achieve proper finishing for every patient after the end of the study.

CONSORT flow chart of the flow of participants in the study.

E] Sample size calculation:

Our sample size calculation is based on a previous study comparing the effect of friction and frictionless mechanics. [14]

F] Recruitment strategy:

The principal investigator will recruit the patients from the clinic of Orthodontic department, Faculty of Oral and Dental Medicine- Future University.

Screening of patients will continue until the total number of participants for the study is collected.

II) Assignment of interventions:

A] Sequence generation:

The supervisor of the study will apply Computer generated random numbers to randomly assign patients to Group A (Friction) or B (Frictionless) using Microsoft Office Excel 2007 sheet. and will write the patient numbers in the first column, and will select function RAND() to generate the randomization number in the second column. These numbers will be sorted according to the randomization number so the first column numbers will be randomly distributed.

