B] Allocation concealment mechanism:

The supervisor of the study will write the randomization numbers of the patients in opaque white papers folded three times to form sealed envelopes and store it inside a box. Then will keep the Codes for randomization at the secretary office.

C] Implementation:

At time of intervention, the main operator will send the patient to the secretary office. Then, the assigned employee will open the box and ask the patient to select one envelope. the main operator will assign each participant for the

corresponding intervention either (friction or frictionless group) according to the list of codes of randomization.

Assignment to either intervention will occur before leveling and alignment stage.

D] Blinding:

Blinding of the operators: Blinding will not be possible for the operators during the application interventions and during the follow up visits. The principal operator is responsible for assigning subjects to interventions according to the concealed allocation, appliance activation at follow up visits, dental impressions and acquisition of dental casts.

Blinding of the outcome assessors: It is a single blinded study, the outcome assessors only will be blind. The patients name will be sealed from pre and post study models. Then two assessors will carry on, blindly and independently, the measurements and analysis of the study.

III) Data collection, management and analysis:

A] Data collection methods:

Primary outcome:

1. Retraction rate: to assess the antero-posterior movement of anterior teeth and first molars, the principle investigator will take study models for every participant monthly during the follow up visits. Then will digitize the models and identify the landmarks, reference lines and planes on the pre, interim and post-retraction digital dental models for measurements reading.

Secondary outcomes:

- 1. Anchorage loss:*** will be accessed by the principal investigator via scanned study models before and after the completion of retraction by identifying the landmarks, reference lines and planes, then will interpret the measurements in degrees and millimeters.
- 2. Pain:*** Each patient will fill a questionnaire regarding his treatment experience in a VAS scoring from 1-10. The questionnaire will include several questions related to oral hygiene, pain and discomfort experienced throughout the trial.

B] Data management:

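### Assignment is placed before a preparation phase common to both arms, so the T0 baseline may be prepared, timed and recorded with the arm known, and patients lost before T0 are randomised without an outcome

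*Combined protocol and SAP*

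**What the plan says.** Section II) C] Implementation gives two timings for the same act. It opens with "At time of intervention, the main operator will send the patient to the secretary office", where the patient draws an envelope, and it ends with "Assignment to either intervention will occur before leveling and alignment stage". The Participant timeline lists allocation as item 5 ("The supervisor will randomly allocate the patients to one of the intervention groups"), the start of the arm-specific treatment as item 6 ("Active intervention will begin after proper leveling and alignment of the upper and lower arches and canine retraction") and the T0 records, taken by the principal investigator, as item 7.

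The Clinical Procedure section sets out bonding, levelling wires, mini-screws, extraction and canine retraction once, for all patients. The two arms get separate instructions only under Beginning of Retraction, after the T0 models. The Study design section likewise has the arms differ only during anterior retraction. Section I) D] Outcomes defines every outcome as a difference between T0 and the end of space closure.

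On roles, the Blinding section states: "The principal operator is responsible for assigning subjects to interventions according to the concealed allocation, appliance activation at follow up visits, dental impressions", and adds the casts. On masking, it states: "Blinding will not be possible for the operators during the application interventions and during the follow up visits". It then says that only the outcome assessors are blind. Under Allocation concealment, the supervisor prepares the envelopes: "Then will keep the Codes for randomization at the secretary office".

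**The concern.** Nothing done before T0 requires anyone to know the arm, yet the explicit timing sentence reveals it at the start of that period. Two things follow.

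First, T0 is triggered by the end of canine retraction, which the text describes only as completed or full. Someone who knows the arm could, without intending to, judge that point differently in the two arms or record the baseline at a different moment. T0 is the starting point for the retraction rate and for every secondary outcome, so an arm-related difference there would enter the comparison.

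Second, a patient who leaves during preparation has been randomised but has no T0 and so no outcome. If the arm is known, leaving can depend on it. If the arm is not yet assigned, it cannot. The protocol gives no analysis set, missing-data rule or drop-out allowance that would deal with such patients.

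**Working it through.** The plan has no figure of its own to reproduce: it states no sample size, power, effect size, standard deviation or drop-out rate. The check is a comparison of the passages plus simple arithmetic with assumed loss rates.

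**1. What lies between assignment and T0.** From Clinical Procedure, under the explicit timing sentence:
- three levelling wires + mini-screws + extraction + canine retraction = 3 + 1 + 1 + 1 = 6 steps
- 7 if bonding and banding also follow assignment
- steps that differ by arm: 0 of 6, or 0 of 7

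This counts exposure. It is not an effect size.

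**2. Who could know the arm.** The main operator makes the assignment ("the main operator will assign each participant for the" corresponding group), and the principal operator takes impressions and casts. The principal investigator takes the T0 records. The documents name nobody for canine retraction and do not say whether operator and principal investigator are one person. Knowledge of the arm at T0 is therefore possible, not documented.

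**3. Which timing applies.** The envelope draw is placed at the time of intervention, and timeline item 6 starts active intervention after canine retraction. Read together, these suggest a late draw. The last sentence of Implementation says the opposite. Item 5 is consistent with early assignment, but it may describe only the supervisor's generation of the list.

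**4. Precision.** Let N be the number enrolled and d the fraction leaving before T0. The expected number reaching T0 is N(1-d) under early assignment and N(1-d) under late assignment, a ratio of 1.00 for any d.

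**5. Randomised patients without an outcome through loss before T0.** Early: N × d. Late: 0. Per 100 enrolled, with assumed d:

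| d | Early | Late | Share of randomised reaching T0, early | Late |
|---|---|---|---|---|
| 5% | 5 | 0 | 95% | 100% |
| 10% | 10 | 0 | 90% | 100% |
| 20% | 20 | 0 | 80% | 100% |

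**6. Chance imbalance.** Assume 40 envelopes, 20 per arm, one per enrolled patient, and loss unrelated to arm. The chance of equal arms at T0 is:
- 4 lost (d = 10%): C(20,2)² / C(40,4) = 36,100 / 91,390 = 0.395
- 8 lost (d = 20%): C(20,4)² / C(40,8) = 23,474,025 / 76,904,685 = 0.305

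The figures are the same whether 4 or 8 assigned patients leave at random or 4 or 8 envelopes stay undrawn in the box. Moving the draw does not change them.

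**The case against.** The strongest reply is that no mechanism for bias is documented. Preparation is identical, so loss could depend on the arm only through knowledge of it, and the plan does not say how that knowledge would change attendance or the timing of T0. Nor can the direction of any shift in the rate be stated. This stands: the point is about an avoidable opportunity, and no bias is shown.

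A second reply is that the assessors are blind. Sealing names on the models protects the reading of a model. It does not protect the state of the mouth when the impression was taken, or the choice of that moment.

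A third is that operators cannot be blinded anyway. The Blinding section says this of applying the interventions and of follow-up visits, and gives no reason for the arm to be known earlier. A reader might infer that early knowledge breaches a blinding commitment. It does not, because the plan reserves blinding for the outcome assessors.

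A fourth is that the arithmetic on randomised patients without outcomes is true by definition, since nobody can be a randomised loss before randomisation. That is fair. It shows what changes in the randomised set, and the loss rates are assumptions.

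Finally, item 5 of the timeline may refer to list generation. The case for early assignment therefore rests mainly on the explicit sentence in Implementation.

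**Conclusion.** The point holds as a design weakness that is cheap to remove. Under the explicit timing sentence, the arm may be known throughout a preparation phase that does not depend on it and while the baseline of every outcome is fixed. Loss in that phase can depend on the arm and leaves randomised patients without an outcome. The two timings in Implementation need reconciling in any case.

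Three stronger readings are not supported.
- **That T0 is biased.** The documents show the opportunity only. The size of any bias cannot be derived from them.
- **That early assignment costs power.** For fixed enrolment, N(1-d) patients reach T0 under either timing. Power falls if the number randomised is held fixed with no allowance for loss, but then late assignment needs more enrolments. For example, with d = 20%, having 32 at T0 takes 32/0.8 = 40 enrolled under either timing.
- **That late assignment balances the arms better by chance.** With the same envelope draw, the chance of equal arms is unchanged (0.395 and 0.305 in the example above). The gain is confined to loss, and a baseline, that cannot depend on the arm.

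The timing conflict and the common preparation are certain from the text. The values of d and the 40-envelope example are assumptions.

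**What to change.** Reconcile the two timings in Implementation by stating that the envelope is opened after the T0 impression and immediately before the T-loop or power chain is fitted. Delete the sentence that puts assignment before levelling. The supervisor may still generate the list early. In the timeline, place the envelope draw after item 7 and state who assigns, since item 5 names the supervisor and Implementation the main operator. Report patients who leave earlier in the CONSORT flow chart as enrolled but not randomised.

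If early assignment must stay, amend Implementation so that the secretary office, which already holds the codes, withholds the arm from the operator until the T0 impression is taken. Report losses before T0 by arm.

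The cost is a formal amendment approved by the department and the Ethics Committee (V) B] Protocol amendments). Patients would also begin treatment before their arm is determined. No extra visit, procedure or staff is needed, and treatment before T0 does not change. If the target counts randomised patients, N/(1-d) must be enrolled to reach it. For 100 randomised, that is 100/0.95 = 105.3 (106), 100/0.90 = 111.1 (112) or 100/0.80 = 125 at assumed d of 5%, 10% and 20%. If the target counts enrolled patients, enrolment does not change.

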 4. Patients with any parafunctional habits.

C] Interventions:

➤ Medical History Questionnaire:

For every patient to exclude the presence of any systemic condition interfering with orthodontic treatment.

➤ Clinical Examination:

Oral structures will be examined to identify caries, fracture or missing teeth. Gingival tissues will be carefully examined for any gingivitis, periodontitis, recession or lesions.

➤ Diagnosis

Check the potential patient to fulfill the previously mentioned inclusion criteria. Every participant will be asked to sign an informed consent about the study. Full set of records (study models, lateral cephalometric radiographs, photos) will be taken for every patient as part of the routine procedure for treatment of patients in the clinic of the Orthodontic Department, Future University.

➤ Clinical Procedure:

After taking pre-treatment records, every patient will undergo:

- Bonding of all teeth except for first premolars, banding/bonding the first and second molars will be done using bidimensional brackets Roth prescription (0.022 slot prescription brackets)
- Levelling and alignment for the bonded and banded teeth will be initiated which will be done by following the wire sequence: 0.014 NiTi , 0.016×0.022 NiTi and 0.017×0.025 StSt.
- Then miniscrews will be placed in upper arch between 2nd premolar and 1st molar.
- The patient will be referred for extraction of 1st premolars then canine retraction will take place on a 0.017×0.025 StSt arch wire.

- Once canine retraction stage is completed, the patient will be referred for the taking of pre-intervention records.

➤ **Acquisition of pre-intervention records:**

- Impressions will be taken followed by digital scanning for the produced stone models which are the T_0 record.

➤ **Beginning of Retraction:**

Frictionless group:

- A ligature wire extending between the canines and mini-screws will be used for proper anchorage control.
- Closing retraction T-loops will be fabricated using 0.017 x 0.025 TMA wire. The loop will be positioned in half the remaining extraction space after canine retraction. [15], [16].
- A gable angle of 45° will be added.
- Distal activation of 4 mm will be done that will produce around 160 g per side of retraction force[17], with cinch back the wire distal to 2nd molars bilaterally.

Friction group:

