- Crimbable hooks added to the arch wire (0.017"x0.025" Stainless steel) distal to the lateral incisor passing through the center of resistance of the anterior segment.
- A ligature wire extending between the canines and mini-screws will be used for proper anchorage control.

- Retraction will start on a 0.017"x0.025" Stainless steel wire with an elastomeric power chain (force applied will be 160 g) extending between the crimpable hooks and the mini-screws.
- The force will be measured by a force gauge and reactivated each visit to maintain force of retraction constant all over the retraction phase.

➤ **Follow up visits**

Patients will be asked to attend for follow up sessions every 4 weeks for:

- Evaluation of the mini implants stability.
- Replacement of the power chain to maintain a force of 160g.
- Reactivation of the T-loop by further distal activation and cinch back.

➤ **Criteria for discontinuing or modifying the allocated intervention:**

In cases of prolonged swelling or pain related to the miniscrew the patient will be given strict oral hygiene measures and may wait for three weeks before the beginning of retraction.

In cases of loose or broken miniscrews, the screw will be removed and replace the miniscrew after total resolution of the inflammation.

➤ **Post-retraction Questionnaire:**

The patients of both groups will be asked to fill in questionnaires regarding their experience with both techniques.

➤ **Retraction records**

The scanned dental models will assess the rate of retraction and molar anchorage loss achieved throughout the study.

➤ **Material Used**

- American Orthodontics Brackets, Roth prescription, Bidimensional slot size.
- American Orthodontics Elastomeric power chains
- American Orthodontics Elastomeric O-ties
- American Orthodontics Ligature wire.
- Jeil, Mini Screws, 8 mm length.
- American Orthodontics Arch wires.
- American Orthodontics Molar bands/tubes.

D] Outcomes

[figure not shown]
Primary outcome: is to monitor the rate of anterior segment retraction using both frictionless and friction methods.

Secondary outcomes is to monitor anchorage loss and pain, in association with each technique after retraction during anterior segment retraction,. All outcomes will be assessed as the difference between T_0 at the start of anterior segment retraction after full canine retraction and T_{final} after complete space closure.

E] Participant timeline:

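### Sealing the patient's name does not blind the assessors to the arm: interim models, and possibly T_final models, can show the T-loop or the hooks and chain

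*Combined protocol and SAP*

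**What the plan says.** Section II.D (Blinding) states that the operators cannot be blinded and then: "It is a single blinded study, the outcome assessors only will be blind". The means given is "The patients name will be sealed from pre and post study models", followed by "Then two assessors will carry on, blindly and independently, the measurements and analysis of the study".

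The arms are told apart by hardware (section I.C, Beginning of Retraction). In the frictionless group, "Closing retraction T-loops will be fabricated using 0.017 x 0.025 TMA wire", and the loop is placed within what is left of the extraction space. In the friction group, crimpable hooks go on the archwire distal to the lateral incisor, with an "elastomeric power chain (force applied will be 160 g) extending between the crimpable hooks and the mini-screws".

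Models come from three stages. For the first, before retraction begins, section I.C says: "Impressions will be taken followed by digital scanning for the produced stone models which are the T_0 record". For the interim stage, the participant timeline (item 9) says: "Each patient will come every 4 weeks for follow up visit, for appliance activation and uptake of impression for interim records". For the last (item 10): "After complete space closure, the principle investigator will take post-retraction records for each participant".

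Section III.A bases the retraction rate on landmarks identified on models from all three stages, and section III.C takes data from the models of every follow-up visit. Both give this work to the principal investigator.

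**The concern.** Since the operators know the allocation, masked measurement is the only safeguard the plan names against measurement bias in the retraction rate and anchorage loss. Landmark placement on a digital model involves judgement. An assessor who can see which appliance is in place may, without intending to, place points in line with an expectation about the faster technique. The background section gives material for such expectations: it describes frictionless mechanics favourably and cites studies in which springs retracted faster, and also one in which the coil-spring side moved further.

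Sealing a name does nothing about this. If the appliance is reproduced in the stone model and its scan, the arm can be read from the object being measured, and the claim of blind assessment would not hold for those models.

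**Working it through.** No arithmetic applies, and the plan gives no figure on this point to reproduce. The check sets what each model can show against what the plan does to hide it.

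| Model | When taken | Can it show the arm? | Masking stated in II.D | Use |
|---|---|---|---|---|
| T0 | After canine retraction, before the retraction appliance is placed | Should not | Name sealed (pre) | Baseline for all outcomes |
| Interim | Four-weekly activation visits | Yes, if loop, or hooks and chain, are in the mouth at the impression | None named | Retraction rate (III.A, III.C) |
| T_final | After space closure | Only if the retraction wire is still in place; not stated | Name sealed (post) | All outcomes |

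1. **Is there any other masking step?** Sections I.C to V.F describe no removal of wires or auxiliaries before impressions, no cropping or masking of scans, no random ordering of models and no check on whether blinding worked.

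2. **Does the coded ID help?** Section V.D puts a coded ID on reports, data and forms, and section III.B counts models as data, so interim models may well be coded. The code serves confidentiality. It hides who the patient is, not which appliance appears on the cast.

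3. **Would the reliability checks catch a shared bias?** The supervisor looks for differences between the two assessors of more than 1 mm. For scale only, the T-loop trial cited in the literature review reports canine retraction of 0.91 and 0.87 mm/month, so the threshold exceeds a month's movement there. In any case, two assessors who both see the appliance can lean the same way and still agree. Repeat measurement a week later has the same limit.

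4. **Who measures?** II.D names two blind assessors; III.A and III.C name the principal investigator. The timeline has that person taking the T0 and T_final records and continuing the treatment, and II.D gives appliance activation and impressions to an unblinded principal operator, apparently the same person. Allocation is known before levelling, so for this person even the T0 models are not measured blind, whatever is masked on the scans.

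**The case against.** The strongest reply is that visibility is inferred. The plan does not say what is in the mouth when an impression is taken. The power chain is replaced at follow-up visits, so it comes off at some point, and the order relative to the impression is not given. This stands as a limit on wording: the models can show the arm, not that they must. It does not remove the concern for interim models, because the hooks are fixed to the archwire and the T-loop is the retraction wire itself, and no step takes either out.

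A second reply is that section I.D defines all outcomes as the change from T0 to T_final, and that III.A uses only before and after models for anchorage loss. If that reading governs, exposure rests on T_final, where visibility is least certain. This also stands in part, but III.A and III.C do use interim models for the rate, and the plan does not rule out hardware at T_final.

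A reader might go further and infer that every model taken after T0 reveals the arm. The documents do not support that for T_final. A reader might also turn the problem into a percentage by dividing some assumed landmark shift by a monthly rate. The plan gives no shift, and the rates at hand are for canines. The effect depends on the interval: a shift of d mm present at T_final but not at T0 changes a rate over k months by d/k, and a constant shift cancels between two consecutive models that both show the appliance. With neither d nor k in the documents, any such percentage would rest on assumption alone.

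**Conclusion.** The point holds in this form: the only masking step that II.D states hides identity and not treatment, so it cannot by itself deliver the blind assessment the plan claims. The inference that the arm can be seen is strong for interim models, conditional for T_final and absent for T0. It assumes that impressions at activation visits are taken with at least the archwire in place, which the plan neither states nor excludes.

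The direction and size of any bias cannot be derived from the documents. What is at stake is the credibility of the retraction rate and, if T_final models show the hardware, of anchorage loss. The change should be made before measurement starts, because measurements already made on unmasked models could be put right only by measuring again. The conflict over who places the landmarks is a distinct weakness, but it has to be settled at the same time: masked scans do not blind someone who treated the patient.

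**What to change.** - **II.D.** State that before measurement all T0, interim and T_final scans are cropped or digitally masked to remove arm-specific hardware: loop, hooks, chain and archwire. Mini-screws may stay, since both arms have them. Keep the crowns and the reference surfaces needed for landmarks and superimposition.
- **Coding and order.** Give each file a random code that keeps one patient's models linkable without showing the arm, and present the patient sets in random order. The colleague outside the research team, who already enters the data under III.B, can hold the code.
- **III.A and III.C.** Have the two blinded assessors, not the principal investigator, place the landmarks and extract the measurements, in agreement with II.D.
- **V.F.** Align the data-access wording, which now admits only the supervisors and the principal investigator, with the roles of the colleague and the assessors.
- **Fallback.** If masking proves infeasible, say in the protocol and the report that assessment is not fully blind.

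The cost is editing time for each scan, a new task for the person who does it, and landmarks that must avoid the masked surfaces. The plan does not name its landmarks, so this last restriction should be checked on a few models first. No patient visit or procedure is added.

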A colleague outside the research team will enter the data and organize it in excel sheets in the computer of the orthodontic department.

Data will include all photographs, models, radiographs and filled questionnaire.

C] Statistical Analysis:

- The principle investigator will be responsible for the extraction of the required data from the study models taken at every follow up visit. The data will be sent to a specialized statistician.
- The specialized statistician will be responsible for the statistical analysis of the study by:
 1. Presenting the data as mean, standard deviation (SD) and Standard error (SE) values.
 2. Using Paired t-test to compare between the friction and the frictionless group of retraction as well as to compare between the pre-and post -treatment data for each group.
 3. Using Kolmogorov Smirnov and Shapiro Wilk tests to determine the rate of anterior segment retraction.

4. Statistically evaluate the patient acceptance for both techniques.

- For this study, the specialized statistician will use IBM11 SPSS12 Statistics Version 20 for Windows to perform the required statistics.
- The significance level will be $P \leq 0.05$. Highly significant variables are detected when P value is less than 0.01.

Assessors Reliability:

- To achieve high reliability for measurements, the supervisor will choose a well-experienced inter-examiner during the study.
- A training session will be provided for the examiners to ensure standard measurements techniques.
- Each examiner will complete the measurements on a model and will repeat the procedure after one week to assess the intra- and inter-examiner reliability.
- The supervisor will compare the measurements of the two assessors for disagreement with a difference of more than one millimeter.
- The supervisor will evaluate the amount of variation in measurements among and between examiners to test the performance of each assessor.
- The examiner with less reliability will receive additional training but will be replaced during the study.
- The specialized statistician will calibrate the intra and inter-examiner reliability for the measurements of the study by Inter-observer and intra-observer reliability was assessed using $P \leq 0.05$.

IV) Method Monitoring:

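### Section II.D gives model measurement to two blinded assessors, but III.A and III.C give landmarking, anchorage-loss assessment and data extraction to the principal investigator, who cannot be taken as blind

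*Combined protocol and SAP*

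**What the plan says.** Section II) D] Blinding calls the trial single blind: "the outcome assessors only will be blind". Operators are stated to be unblinded when the intervention is applied and at follow-up visits. The masking step is: "The patients name will be sealed from pre and post study models". After it comes the assignment of the work: "Then two assessors will carry on, blindly and independently, the measurements and analysis of the study".

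Section III) A] Data collection methods describes the same work differently. For the retraction rate, "the principle investigator will take study models for every participant monthly during the follow up visits". The next sentence keeps that subject: "Then will digitize the models and identify the landmarks, reference lines and planes on the pre, interim and post-retraction digital dental models", for measurement reading. Anchorage loss "will be accessed by the principal investigator via scanned study models before and after the completion of retraction", by means of landmarks, lines and planes, and the same person "then will interpret the measurements in degrees and millimeters".

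Section III) C] Statistical Analysis adds: "The principle investigator will be responsible for the extraction of the required data from the study models taken at every follow up visit". The data then go to a statistician.

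The Assessors Reliability text that follows again assumes two examiners who measure, repeat after one week and are compared with each other.

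**The concern.** Blinding of the outcome assessors is the only blinding the trial claims. Both the primary outcome (retraction rate) and the secondary outcome anchorage loss are distances read from digital models, and those distances depend on where landmarks and reference planes are placed. If someone who knows the arm places them, or takes the readings, knowledge of the arm can enter the result even though the plan describes blinded assessment. Staff who follow III.A and III.C as written would depart from II.D without breaking any other instruction in the protocol.

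**Working it through.** No arithmetic applies, and the plan states no figure on this point to reproduce. The check sets the sections side by side.

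**Step 1. Who does what.**

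| Task | II.D | III.A | III.C |
|---|---|---|---|
| Taking the models | Principal operator (impressions and casts) | Principal investigator, monthly | not stated |
| Digitizing and landmarking | not stated separately | Principal investigator | not stated |
| Measuring for the retraction rate | Two blinded assessors | Reader not named | Principal investigator, if extraction means measuring |
| Assessing and interpreting anchorage loss | Two blinded assessors | Principal investigator | Principal investigator, if extraction means measuring |
| Compiling the data | not stated | not stated | Principal investigator, if extraction means compiling |

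**Step 2. Can the principal investigator be taken as blind?** III.A has this person take models at the follow-up visits. Item 9 of the Participant timeline makes these the four-weekly visits for appliance activation as well as impressions. Under C] Interventions, the power chain is replaced or the T-loop reactivated at those visits. Items 7, 10 and 12 of the timeline also have the principal investigator take the records before and after retraction and continue each patient's treatment. Nothing says that this person is masked, or is one of the two assessors.

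**Step 3. How far the contradiction reaches.**
- *Anchorage loss:* II.D gives measurement to the assessors; III.A has the principal investigator assess and interpret it. Both cannot hold.
- *Retraction rate:* III.A can mean that the principal investigator prepares the models and the assessors then read them. II.D would then hold for the reading, but the landmarks and planes that fix the distances would still come from someone not shown to be blind.
- *Data extraction:* III.C can mean measuring, which clashes with II.D, or compiling the assessors' readings, which does not.

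**Step 4. Would the planned checks show a problem?** The one-week repeats, the comparison of the two assessors and the supervisor's review compare the assessors with themselves or with each other. If both read from landmarks already placed by the principal investigator, they share any error in those landmarks, and the checks may not reveal it.

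**Step 5. Does the masking suffice for the assessors?** II.D seals names on the pre and post models only, while III.A also uses interim models. Sealing a name does not hide a T-loop, crimpable hooks or a power chain. The T0 models are taken before these are fitted; for later models the documents do not say whether the hardware is removed before the impression or would show on the cast.

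**The case against.** The strongest reply is that II.D governs and III.A and III.C are loosely worded. On that view the principal investigator prepares the models and is answerable for the data, while the assessors measure. The reliability text supports it in part: examiners are trained in measurement technique and complete the measurements on a model themselves, which is compatible with their placing their own landmarks. This stands as a possible reading for the retraction rate and for data extraction. It does not fit anchorage loss, where III.A names the principal investigator and includes interpretation of the measurements. Nor does it remove the investigator's landmarking for the rate, which III.A states.

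V) D] Confidentiality also puts a coded ID on reports, data and administrative forms. If models count as data, as III) B] Data management suggests, interim models may be coded too. That softens the complaint about names, but it neither blinds the principal investigator nor hides hardware from the assessors.

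A reader might infer three stronger things that the documents do not support:
- That the primary outcome is certain to be assessed unblinded. That depends on which reading of III.A is followed.
- That the principal investigator and the unblinded principal operator are stated to be one person. Their duties overlap, so it is a reasonable inference, but the documents never say so and the point does not need it.
- That following II.D would fully blind both model-based outcomes. That is not shown, because of the visible hardware.

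Pain is scored by the patients, who are not blinded, and is the same under every reading. It adds nothing to this point.

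**Conclusion.** Wrong as written: an internal contradiction over who carries out outcome assessment. It is outright for anchorage loss. For the retraction rate it turns on how III.A is read, but even the favorable reading leaves landmark placement with someone who cannot be taken as blind, so bias in the primary outcome remains possible. For data extraction it depends on what extraction means.

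The size and direction of any bias cannot be estimated from the documents. The conclusion rests on two assumptions: that a person taking models at activation visits sees which appliance is in use, and that landmark and plane placement involves observer judgment. Both are plausible; neither is stated in the plan. The point should be settled before models are measured, because it concerns the only blinding claimed and can be corrected by rewording and reassigning work.

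**What to change.** - **III.A and III.C:** assign identification of landmarks, lines and planes, all measurement including anchorage loss, and data extraction to the two blinded assessors already named in II.D, each working independently. Limit the principal investigator to taking and scanning the models.
- **II.D:** extend masking from the pre and post models to every model used in an outcome, by means of coded scans. Crop or cover hardware that reveals the arm (T-loop, crimpable hooks, power chain) on the scans where possible. Where it is not possible, state that blinding is partial.

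The cost is more measurement time for the two assessors and some time to code and prepare the scans. Treatment and the visit schedule do not change.
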